### **Provisions for Research Related Injury**

Because the risk profile of tDCS is very low, no research-related injury is anticipated. In the unlikely event that a patient reports clinically-relevant harm from the study, this information will be conveyed to one of the study physicians ([name], MD; [name], MD), who will evaluate the patient. The physician will ensure that the patient has appropriate medical follow-up. The IRB guidelines for reporting will be followed.

## **REGULATORY AND ETHICAL OBLIGATIONS**

### **General**

This study will be conducted in accordance with the ethical principles that have their origin in the Declaration of Helsinki and under applicable regulatory requirements; the Code of Federal Regulations (CFR), CFR Title 21, International Conference of Harmonisation (ICH) Good Clinical Practice (GCP) E6.

### **Protocol**

A copy of the protocol, proposed informed consent, research authorization and any further documentation will be submitted to the Institutional Review Board (IRB) for written approval. All subsequent protocol amendments and changes to the informed consent document will be submitted to the IRB for written approval.

### **Informed Consent**

Each qualified participant will voluntarily sign and date the informed consent and research authorization after the study purposes, procedures, and potential risks and benefits of the study and all other aspects have been fully explained to them. The consent form must be signed prior to performance of any study-related activity.

### **Confidentiality**

All medical information collected from study participants, and documentation related to their participation in the study will be kept in a locked cabinet at MJHS Institute for Innovation in Palliative Care. Unique patient identifiers will be used to label all data. Strict standards of confidentiality will be upheld at all times.

### **Alternatives to Participation**

The alternative to participate in this study is not to participate. Participants are free to withdraw at any time without penalty. Participants may elect to discuss possible approaches to symptom management in chronic illness with their medical providers.

### **Prompted Action**

If the score on the Hamilton Depression Scale (Ham-D) is 17 or higher [moderate or severe depression], the study personnel will ask the patient whether he/she would like to have study personnel contact the patient's physician to inform him/her about this score.

If the score on item #3 of the Ham-D scale is 3 or 4 [Suicidal ideas, gestures or attempts], the patient will be told that the study physician will be informed, and that the study physician will make a determination about whether to inform the patient's physician that this score was elicited.

## **ADMINISTRATIVE ISSUES**

### **Compensation**

Participants who undergo the study intervention in accordance with the study protocol (daily active/sham tDCS with completed Daily Diaries and completed outcome assessment questionnaires), will receive monetary compensation for their time and effort up to \$150 in cash dispensed at Visit #3.

Participants not adhering to the study protocol will not receive the compensation.

Participants who do not start the at-home stimulation phase will not be compensated. This means that participants who complete the 30-day Baseline phase and do not qualify will not be compensated for their time.

Participants who start the at-home stimulation phase, but leave the study early, will receive prorated compensation as it follows:

- If they leave the study before completing the first month of stimulation, they will receive \$50, if they followed the study procedures (tDCS daily applications, Daily Diaries and questionnaires).
- If they complete the first month of at-home stimulation, but not the second month of at-home stimulation, they will receive \$100, if they followed the study procedures.
- If they complete both the first and second month of at-home stimulation, you will receive \$150, if they followed the study procedures.

### **Study Registration**

The study will be registered at the publicly accessible website ClinicalTrials.gov. in accordance with the U.S. regulatory requirements.

### **Study Documentation and Storage**

A list of all persons authorized to perform study procedures will be maintained in the Regulatory Binder. All study related essential documentation will also be kept in the Regulatory Binder. Participant's study files and source documentation will be maintained by the assigned study staff. Study files will be kept locked in the research offices. Following completion or termination of the study, all study documents will be kept for a minimum of 3 years as required by the IRB.

## Analysis Plan (Update 1.29.20)

Participants will be randomized within randomly selected blocks of sizes 2, 4, and 6. The randomization list will be generated by an investigator not otherwise associated with the administration of treatment or collection of data.

All patient characteristics and outcomes will be evaluated for distribution. For all bivariate tests, the appropriate parametric or non-parametric test will be selected based on distribution. Patient characteristics will be described and bivariate tests will evaluate any differences across treatment group (active tDCS vs. sham tDCS). Primary and secondary outcomes at baseline will be described and bivariate tests will evaluate any differences across group. Bivariate tests will evaluate differences in attrition, patient satisfaction, adverse events (including all adverse events, serious adverse events, and adverse events attributed to the treatment), and quality of blinding across group.

All outcomes will be described using data visualization. Differences in outcome between the active tDCS and sham tDCS groups will be evaluated in both intent-to-treat and completer analysis using non-parametric statistics as appropriate (see Table below). Intent-to-treat analysis will impute missing values using all available data. Differences in outcome between people with chronic (15 or more headache days/month) vs. episodic migraine, with and without medication overuse (e.g., using a MSM on 10 or more days per month during the baseline period), and with high and low levels of patient compliance will also be evaluated using the appropriate non-parametric statistic.

Alpha will be set at 0.05, two-tailed, for all analyses. SPSS v. 25.0 and R will be used for all analyses.

Primary Outcome	Description	Tentative Analysis Type
Change in migraine day/30 day	Median change in the number of migraine days per 30 day period, from M0 to M2.	Mann-Whitney U
Secondary Outcomes		
Responders	% of participants who report a 50% reduction in migraine days, from M0 to M2.	Fisher's Exact Test
Change in headache attack/30 days	Median change in number of attacks per 30 day period, from M0 to M2.	Mann-Whitney U
Change in acute medication use	Median change in number of days on which an acute medication was used from M0 to M2.	Mann-Whitney U
Change in headache attack intensity	Median change in NRS from headache days in a 30 day period from M0 to M2.	Mann-Whitney U

Change in Migraine-Specific Quality of Life – Total, and 3 subscales	Median change in MSQ score from M0 to M2	Mann-Whitney U
Change in Hamilton Depression Scale	Median change in Ham-D score from M0 to M2	Mann-Whitney U
Tolerability	Side effects AEs Total AEs related in any degree to the treatment	Mann Whitney Us
Satisfaction	% of participants who report being satisfied with the treatment	Fisher's Exact Test

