### **Inclusion Criteria**

- Age 18 - 65 years;
- Has episodic or chronic migraine with or without aura, diagnosed according to the International Classification of Headache Disorders 3rd edition (ICHD-3) criteria, for at least the past 12 months;
- Migraine occurring on 4 or more days per month, as documented through the 30-day baseline;
- No change in prophylactic therapy in 3 months preceding the baseline;

- If on antidepressant, blood pressure or epilepsy medication for reason other than migraine, the medication regimen is stable for at least 3 months preceding the baseline; Able to follow instructions in English;
- Understand the informed consent process and provide consent to participate in the study.

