**Visit #1:** The visit will take place at a designated room at the New York Headache Center. At the visit, the study staff will guide the patient through the process of review and signing the Informed Consent and HIPAA authorization to allow study staff to obtain necessary medical information from patient's medical record. The patient will receive a copy of the signed Informed Consent and HIPAA authorization. Study staff will then collect profiling demographic and clinical characteristics and review medical information for the purpose of eligibility screening. Patients who meet the study Inclusion/Exclusion criteria at screening will receive instructions on how to keep Participant's Daily Diaries and will proceed to the baseline.

**30-day Baseline (at home):** Through the baseline, patients will keep daily diaries to document migraine occurrence, related symptoms and medication intake. The diaries will be sent once a week via encrypted HIPAA-compliant email or by fax to the study personnel. Patients who report 4 or more migraine days per month at the end of the baseline period and fully meet the Inclusion/Exclusion criteria will be eligible to undergo randomization and proceed to the interventional phase of the study.

**Randomization.** Randomization list will be computer generated by study statistician using the block-of-six method. Both the patient and study personnel, except for statistician will be blinded to the sham vs active tDCS treatment assignment. tDCS devices will be programmed to sham or active tDCS mode in accordance with the randomization list.

**tDCS stimulation protocol and device.** The active tDCS will involve 20-minutes of direct current at intensity of 1.5 mA. Sham will include 30 seconds of stimulation at 1.5 mA, followed by 0 mA for the remaining time. The stimulation pads (electrodes) will be placed in a simple headband, as depicted in detail in the Patient tDCS Instructional Brochure. The tDCS device for this study will be *Soterix mini-CT* (Soterix Medical Inc., New York, NY). The tDCS mini-CT was developed for at home administration and has enhanced safety features: a unique keypad access system that allows the user to apply only the pre-determined dose each day. The device will be deployed to the patient at Visit #2.

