## **SAMPLE SIZE DETERMNATION AND DATA ANALYSIS**

The sample size calculations are based on responder rates from previous studies of non-invasive neurostimulation in migraine (Lipton et al., 2010; Saper et al., 2011). The numbers used were 15% for sham, based on published trials and 55% for the supraorbital neurostimulation inferred from the pilot study (Gerardy et al., 2009; Lipton et al., 2010; Saper et al., 2011) and 12.1% for sham vs 38.1% for verum in the RCT (Schoenen et al., 2013). To detect a significant difference between the 2 treatments (5% significance level) with an 80% power, the minimum size of each treatment group was estimated at 26 patients, 52 in total who get randomized and initiate the intervention. To account for possible dropouts in the category "randomized, but never started the intervention", we plan to randomize in total 60 patients. To account for patients who do not meet the eligibility criteria at screening, we anticipate we will need to consent about 75 patients.

Statistical analysis will be carried out on an intention-to-treat basis, as well as per protocol for comparison. For Aim 1, the primary comparison will be the between-group comparison at the end of month 2 of the tDCS/sham intervention for the primary and secondary outcomes measures (listed in detail on pgs 7,8). Secondary exploratory comparisons will include between-group comparisons at the month 1 (Day-30) of the 2-month intervention, and within groups comparisons across the study time-points (the baseline, month 1, month 2), as well as comparison of efficacy in patients with chronic and episodic migraines and comparison of efficacy in patient taking abortive migraine medications on 10 or more days with those taking them on 9 or fewer days.

For Aim 2, (Satisfaction with the device and procedure), the primary analysis will include the between-group comparison of at the end of month 2 of the tDCS/sham intervention, evaluating the percentage of patients stating at the end of the trial that they are very satisfied, moderately satisfied, or not satisfied with the device use and procedure, determined from the 8-item tDCS User Survey at the end of the intervention. (We anticipate significant group differences in Survey items pertaining to being more confident in symptom management at home, but no significant group differences in items pertaining to satisfaction with tDCS training and ease of use of the device). In addition, the

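### The primary test ignores baseline migraine frequency, and allocation is not stratified, in a trial that mixes episodic and chronic migraine with no upper limit

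*SAP*

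**What the plan says.** **Who enters.** The Protocol's Inclusion Criteria admit a patient who "Has episodic or chronic migraine with or without aura, diagnosed according to the International Classification of Headache Disorders 3rd edition (ICHD-3) criteria". The frequency criterion is "Migraine occurring on 4 or more days per month, as documented through the 30-day baseline". Neither the inclusion nor the exclusion list sets an upper limit.

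**Allocation.** The Protocol (Randomization paragraph) says "Randomization list will be computer generated by study statistician using the block-of-six method". The SAP says "Participants will be randomized within randomly selected blocks of sizes 2, 4, and 6". The two differ on block size and on who prepares the list, and should be reconciled. Neither names a stratification factor.

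**Primary analysis.** The SAP table gives a Mann-Whitney U test on change in migraine days per 30 days from baseline to month 2, under a column that labels the analyses tentative. No covariate or stratum is named. The SAP compares baseline outcomes between arms but does not say what follows if they differ.

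**Chronic versus episodic.** The Protocol places "comparison of efficacy in patients with chronic and episodic migraines" among its secondary exploratory comparisons. The SAP repeats it as "Differences in outcome between people with chronic (15 or more headache days/month) vs. episodic migraine", which fixes the cut.

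**Timing.** In the procedural schema, the 30-day baseline diary and the confirmation of eligibility both come before randomisation. The diary records migraine and other headaches, so the SAP's cut can be counted for each patient before allocation.

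**The concern.** The primary outcome is an absolute fall in days. A patient who starts at 5 migraine days cannot lose more than 5, while one who starts at 20 can lose far more. Baseline count is therefore likely to explain much of the spread in the outcome, and it is known for every patient before allocation. The plan uses it neither in the allocation nor in the test.

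Two things are at stake. First, between-patient variation that could be removed stays in the comparison and costs power. Second, if one arm happens to receive more high-frequency patients, the unadjusted result of that one trial moves: towards a false benefit if they fall in the active arm, or towards masking a real one if they fall in the sham arm. Blocking balances the arm totals, not the mix of patients within them.

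**Working it through.** **1. The plan's own figure.** The Protocol states 26 per group from responder rates of 15% and 55%, with 5% significance and 80% power. Taking the test as two-sided (SAP):

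- Uncorrected n = [1.96·√(2·0.35·0.65) + 0.8416·√(0.15·0.85 + 0.55·0.45)]² / 0.40² = (1.322 + 0.515)² / 0.16 ≈ 21.1, so 22.
- With continuity correction: (21.1/4)·[1 + √(1 + 4/(21.1·0.40))]² ≈ 25.9, so 26.

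The figure reproduces. It concerns responders, and the documents give no power figure for the primary test on change in days. The fix below does not alter it.

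**2. Chance of an uneven chronic split.** The Protocol says "we plan to randomize in total 60 patients". I assume 30 per arm, which the blocks and equal group sizes imply. With m chronic patients among 60, the number k in one arm is hypergeometric:

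P(k) = C(m,k)·C(60−m, 30−k) / C(60,30)

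I sum over all k where one arm holds at least twice as many as the other. For m = 12 (8:4 or worse): 2 × (0.1146 + 0.0415 + 0.0093 + 0.0012 + 0.0001) = 0.333.

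The documents do not give m. Their only population figures are 3 of 36 million Americans (3/36 × 60 = 5) and a cited cross-sectional study that was 91% episodic (0.09 × 60 ≈ 5.4). Most referrals come from a specialist headache centre, which may raise the share. Over an assumed range:

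| Chronic of 60 (assumed) | Chance of 2:1 or worse |
|---|---|
| 5 | 35% |
| 12 | 33% |
| 15 | 23% |
| 20 | 5% |
| 30 | 2% |

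The chance does not fall smoothly, because counts are whole numbers (67% at 6, 30% at 10). Simulated unstratified lists with blocks of six, and with random blocks of 2, 4 and 6, agree with these values to within about half a point, so blocking alone gives no protection.

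**3. What a split does to one trial.** Assume a chronic baseline of 15–28 days, an episodic baseline of 4–14, no device effect, and a mean reduction of 25% (SD 25 points) in both arms. The Mann-Whitney test then falsely favours active in 1.9% of trials with a 6:6 split. When active holds the larger share, this becomes 4.7% at 8:4, 5.3% at 10:5 and 8.9% at 14:6, against a nominal 2.5%. The spurious mean difference is 0.4, 0.5 and 0.8 days respectively.

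**4. What it does in the long run.** Averaged over all splits, the two-sided type I error stays at about 5%.

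**5. What recovers power.** With the same baseline ranges and an assumed 18-percentage-point effect:

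- Stratifying the list but keeping the plain Mann-Whitney test: no clear gain (within about 2 points).
- Stratified rank test: about 3 to 9 points more power.
- Rank adjustment for baseline migraine days: about 10 to 15 points more power.

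**6. What stratified lists add.** Blocks of at most 6 within the chronic stratum hold the arm difference there to 3 patients. In simulation with blocks of 2, 4 and 6, the chance of a 2:1 split was 0% at 12, 15, 18 and 20 chronic patients, about 2% at 9 and about 15% at 6.

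**The case against.** Unstratified blocked randomisation is valid. The test's error rate already allows for chance imbalance, and nothing in the documents is contradictory on stratification. Under a second set of assumed values (mean change −5 days, SD 5, in chronic patients; −2, SD 3, in episodic; 12 chronic; a 2.5-day effect), power was 76% unstratified and 77% stratified. All of this stands, and it is why a stratified list alone is not the remedy. It does not answer the power lost by leaving baseline out of the test. Under those same values an 8:4 split moved power to 87% or 63%, depending on its direction.

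The outcome is already a change from each patient's own baseline, and baseline values will be compared between arms. That is true, but subtracting the baseline does not remove the dependence of the fall on the starting count, and no adjustment follows from the comparison.

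The chronic/episodic comparison is exploratory, and low numbers weaken it more than an uneven split does. This also stands. An 8:4 split raises the variance of the treatment comparison within chronic patients by only (1/8 + 1/4)/(1/6 + 1/6) − 1 = 12.5% over 6:6. With about 5 chronic patients, 3:2 is hardly more informative than 4:1.

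The Protocol's Background says that the two forms are not biologically distinct. It also says that they differ by attack frequency, which is what bounds the primary outcome.

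**Conclusion.** The point holds as a matter of efficiency and robustness, and it is minor. The primary analysis leaves out a strong prognostic variable that is known for every patient, and allocation does nothing to balance it. The cost is lost power, put at about 10 to 15 points relative to rank adjustment under the stated assumptions, plus exposure of one small trial to an unlucky split. These power figures rest on assumed baseline ranges and an assumed effect, and will shift with both; the split probabilities rest on an assumed chronic count.

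A reader might infer three stronger things that the documents do not support:

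- **That the comparison is biased or the test invalid.** It is not, on average.
- **That a lopsided chronic split is likely.** The chronic share is not given, and the chance runs from about 35% at 5 patients to 2% at 30.
- **That the missing stratification is what makes the chronic/episodic comparison uninterpretable.** That comparison is exploratory, and its weakness comes mainly from its size.

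**What to change.** **Main change.** Before unblinding, replace the plain Mann-Whitney U for the primary outcome with one named test that accounts for baseline:

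- rank ANCOVA (or an equivalent model) of the change in migraine days on arm, adjusting for baseline 30-day migraine days; or
- a van Elteren (stratified Wilcoxon) test by chronic/episodic status, using the SAP's cut of 15 or more headache days, counted in the 30-day baseline diary.

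The first addresses the starting count directly and gained more in the check above; the second stays closer to the present test. A cut at 15 leaves variation within the 4–14 range unadjusted.

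**If allocation has not begun.** Also prepare separate blocked lists for chronic and episodic patients, assign the stratum when eligibility is affirmed, and use the same definition in the exploratory comparison. This modestly helps that comparison.

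**Cost.** No added patients. The primary test is slightly more complex. Stratified lists need one extra list and one field on the eligibility form, and because each stratum can end on an incomplete block, overall arm sizes may differ by a few patients. If allocation has begun, the change of test is still available on its own.

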## **OUTCOME MEASURES AND ENDPOINTS**

Outcome assessment time-points will be at the end of the 30-day baseline ( $\pm 2$  days), at the end of month 1 (day  $30 \pm 2$  days, the secondary end-point) and month 2 (day  $60 \pm 2$  days, the primary end-point) of the tDCS/sham intervention.

The primary comparison will be the between-group comparison at the end of month 2 of the tDCS/sham intervention.

**The primary outcome measure** will be *Change in mean number of migraine days per month.*

A note: A migraine day is defined as any calendar day on which the patient had onset, continuation, or recurrence of a migraine as recorded in the diary. A migraine is defined as a migraine (with or without aura) lasting at least 30 minutes. Any calendar day on which acute migraine medication is used is counted as a migraine day.

**Secondary outcome measures** will be:

1. *Percentage of responders*, determined as a number of patients having at least 50% reduction of monthly migraine days between the one-month baseline and post-intervention, in each of the two study groups;
2. *Change in monthly migraine attack frequency*,
3. *Change in monthly acute antimigraine drug use*,

all determined from the patients' diaries;

4. *Change in mean headache severity per migraine day* determined from Pain NRS ratings on migraine days;
5. *Change in quality of life* determined from ratings on the migraine-specific MSQ questionnaire;
6. *Change in depressive symptoms* determined from the Hamilton Depression Scale (HamD);
7. *Tolerability* determined from occurrence of side effects and adverse events related, probably related or possibly related to tDCS, through the study;
8. *Satisfaction* - percentage of patients stating at the end of the trial that they are very satisfied, moderately satisfied, or not satisfied with the treatment, determined from the 8-item tDCS User Survey at the end of the intervention;

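### Adverse events are compared between arms by hypothesis tests with no effect estimate or interval, and the test for serious events is not fixed

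*SAP*

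**What the plan says.** Safety compared with sham is part of Aim 1 (Protocol, Objectives and Specific Aims). Tolerability is the seventh secondary outcome, "determined from occurrence of side effects and adverse events related, probably related or possibly related to tDCS, through the study" (Protocol, Outcome Measures and Endpoints).

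The SAP (Analysis Plan, Update 1.29.20) handles safety in two places:

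- The text plans bivariate between-arm tests of "adverse events (including all adverse events, serious adverse events, and adverse events attributed to the treatment". It names no test for them: "For all bivariate tests, the appropriate parametric or non-parametric test will be selected based on distribution".
- The outcome table has a tolerability row covering side effects, AEs and "Total AEs related in any degree to the treatment". The method given is "Mann Whitney Us", in a column whose heading marks the choices as tentative. Serious events have no row.

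Two general statements also apply: "Alpha will be set at 0.05, two-tailed, for all analyses" and "All outcomes will be described using data visualization". Fisher's exact test is named only for responders and satisfaction. No between-arm estimate or interval is planned for adverse events, and nothing says whether patients or events are counted.

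**The concern.** The trial was sized for a 40-point difference in responder rates. Harms that matter for a device used daily at home may be much rarer. At that size a test of adverse events has little power against uncommon harms, and a p-value alone does not show the reader how large an excess remains possible.

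Two further gaps add to this. Because the test for serious events is to be chosen after the data are seen, the same data can be called significant or not according to that choice. And because the counting unit is undefined, the protocol's notion of occurrence could be analysed either as patients affected or as events per patient. For common mild effects those are different questions.

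**Working it through.** **Inputs.** Two-sided alpha 0.05 (SAP). 60 randomised, with a minimum of 26 per group (Protocol, Sample Size). Equal allocation is assumed: the ratio is not stated, but 26 per group and 52 in total imply it. At most one event per affected patient unless stated. The event rates below are illustrative, since the documents give no expected adverse-event rates by arm.

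**The plan's own figure.** For 15% vs 55%, 80% power, two-sided 5%:

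n = [1.960·√(2·0.35·0.65) + 0.842·√(0.15·0.85 + 0.55·0.45)]² / 0.40² = (1.322 + 0.515)² / 0.16 = 21.1, so 22 per arm.

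With continuity correction: (21.1/4)·[1 + √(1 + 4/(21.1·0.40))]² = 25.9, so 26 per arm. The stated 26 is reproduced. It concerns responders; no figure is given for safety.

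**One-sided splits, 30 per arm (k vs 0 patients).**

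Fisher, two-sided: 2·C(30,k)/C(60,k). For k = 3, 2·4,060/34,220 = 0.237. For k = 5, 2·142,506/5,461,512 = 0.052.

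Mann-Whitney, tie-corrected normal approximation with continuity correction. For k = 5, U = 525, its null mean is 450 and its SD is 32.38, so z = (75 − 0.5)/32.38 = 2.30 and p = 0.021.

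| Patients affected | Mann-Whitney p | Fisher p |
|---|---|---|
| 3 vs 0 | 0.081 | 0.237 |
| 4 vs 0 | 0.042 | 0.112 |
| 5 vs 0 | 0.021 | 0.052 |
| 6 vs 0 | 0.011 | 0.024 |

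The first significant split is 4 vs 0 under Mann-Whitney and 6 vs 0 under Fisher. At 26 per arm the pattern is the same (5 vs 0: 0.021 and 0.051). For 5 vs 0 at 30 per arm, Pearson chi-square (0.020), Barnard (0.035) and Boschloo (0.022) also reject, while the Yates-corrected chi-square (0.062) does not. Fisher is sensitive to slight imbalance: 5/29 vs 0/31 gives 0.022, and 5/31 vs 0/29 gives 0.053.

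**Power, 30 per arm, patients with at least one event.** When one arm has a true rate of zero, power is the chance of reaching the first significant split: P(X ≥ 4) for Mann-Whitney and P(X ≥ 6) for Fisher, with X binomial (30, p). The third row is by enumeration of all outcomes.

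| True rates | Mann-Whitney | Fisher |
|---|---|---|
| 0% vs 5% | 6% | 0.3% |
| 0% vs 10% | 35% | 7% |
| 5% vs 20% | 45% | 24% |

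At 26 per arm Mann-Whitney gives 4%, 26% and 40%.

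**What an interval would show.** With no events in n patients, the exact two-sided 95% upper limit is 1 − 0.025^(1/n): 11.6% at n = 30 and 13.2% at n = 26.

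The Newcombe interval for a risk difference d uses the Wilson limits of each arm (l₁, u₁ and l₂, u₂): d − √[(d − l₁)² + (u₂ − p₂)²] to d + √[(u₁ − d′)² + (p₂ − l₂)²], where p₂ = 0 here and so d′ = p₁ = d. The Wilson limits for 0/30 are 0 and 11.4%.

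- 5/30 (Wilson 7.3% to 33.6%) vs 0/30: 16.7 points, 95% CI 2.0 to 33.6.
- 3/30 (Wilson 3.5% to 25.6%) vs 0/30: 10.0 points, 95% CI −3.1 to 25.6.

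The second split is non-significant under both tests, yet an excess of about 25 points is not excluded.

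**Counting unit.** Five events on active and none on sham gives Mann-Whitney p = 0.021 if they fall in five patients, 0.081 if in three, 0.161 if in two and 0.334 if in one (30 per arm). An event total alone does not determine the result.

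**The case against.** The strongest reply is that Mann-Whitney U is the only test the SAP names for adverse events, and under it a large excess is detected. A reader might infer that five patients with a serious event on active against none on sham would be reported as no significant difference. The documents do not support that: it holds under Fisher or Yates with equal arms, and Fisher is assigned only to other outcomes. Under Mann-Whitney that split is significant. This stands, and it rules out describing the tests as blind to harm in general.

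It is also fair that safety is not judged by p-values alone. Outcomes are to be plotted, and the Protocol's Safety Monitoring Plan has adverse events recorded, followed by the study physician and reported to the IRB. That is oversight of individual events, however. It does not supply a between-arm estimate.

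Two further inferences go beyond the text. No passage says that non-significance will be read as evidence of safety. Nor does any passage say that a sensation felt at each of the 60 daily applications will be logged 60 times. The Protocol describes mild tingling as a natural sensation of the current, so it may not be recorded as an event at all. The SAP leaves repeated counting open and does not prescribe it.

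Last, between-arm estimates with intervals are absent for every outcome in the SAP table, so the point is partly general. It carries more weight for safety, where a non-significant result is likely even when a real difference exists.

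**Conclusion.** The point holds in a limited form. The planned between-arm safety analysis consists of tests at 0.05 plus plots, with no estimate or interval. The test for serious events is open, and that choice alone moves 5 vs 0 from p = 0.021 to p = 0.052. Even under the more favourable test, each of the three scenarios examined would more likely than not be missed (power 6%, 35% and 45% at 30 per arm), so a non-significant result would be weak evidence about safety.

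This rests on 1:1 allocation, 26 to 30 patients analysed per arm, a patient-level analysis for the power figures, and illustrative event rates. It does not rest on any claim about how the sponsor would interpret the tests. The matter should be corrected, but it does not affect the primary efficacy analysis.

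**What to change.** In the SAP, make the safety analysis a table of patients with at least one event in each arm, as number and percentage, for side effects, any AE, serious AEs and related AEs. Give the risk difference and a 95% confidence interval for each, with the interval method named in advance. Newcombe is one option. Its interval for 5/30 vs 0/30 excludes zero although Fisher gives 0.052, which is a reason to fix the method beforehand.

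Give event counts as description only. If any test is kept, name it for each event category, including serious events. Add a sentence that no safety conclusion rests on a non-significant test.

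The cost is SAP wording and one table; no extra patients or data collection are needed. The downside is that the intervals will be wide and visibly so.
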